MELT-HF

**MEtolazone as Early add on Therapy for acute
decompensated Heart Failure.**

A single center pilot study.

[name]

INTRODUCTION

Background

- ▣ Heart failure is a major source of morbidity, mortality and growing public health cost.
- ▣ In US, the number of congestive heart failure patients is more than 4 million with more than 550,000 new annually reported cases.
- ▣ The annual cost of heart failure management exceeds 35 billion dollars per year.
- ▣ The heart failure readmissions and average length of hospital stay cost approximately \$11,000 per patient.
- ▣ Loop diuretics are used alone in the majority of cases to promote diuresis.
- ▣ An association of increased creatinine and increased risk of renal dysfunction, the cardiorenal syndrome, in the face of high dose loop diuretics has raised questions regarding the safety and toxicity of high dose loop diuretics.
- ▣ While the dose of diuretics is ubiquitous, little data exists to guide their use and many clinicians are uncertain as to when and how to initiate and limit therapy.
- ▣ In many cases, a “stepped approach” with oral loop diuretics advancing to intravenous and finally combination high dose diuretics is employed.

PREVIOUS TRIALS

DOSE(Diuretic strategies in patients with ADHF) Trial

- ▣ Prospective, randomized double blinded trial of 308 patients with ADHF.
- ▣ Showed that high dose diuretics (2.5 times the outpatient daily dose) were associated with improved urine output at 72 hours (3575 ± 2635 in low dose group vs. 4899 ± 3479 in high dose group).
- ▣ There was no significant difference between the high and low dose groups in mean creatinine change (0.08 ± 0.3 mg per deciliter in high-dose group as compared to 0.04 ± 0.3 mg per deciliter in low-dose group, $P=0.21$).

CARESS-HF (Ultrafiltration in ADHF patients with CRS) Trial

- ▣ Randomized non blinded study of 188 patients with ADHF.
- ▣ High dose loop strategy with stepped addition of metolazone was used. The combination approach compared favorably with renal ultrafiltration in patients with acute decompensated heart failure.

- ▣ At 96 hours, the mean change in the creatinine level was 0.04 ± 0.53 mg per deciliter in drug therapy group, as compared with $+0.23 \pm 0.70$ mg per deciliter in the ultrafiltration group ($P = 0.003$).

The above adverse effects will be collected on each patient for 48 hours after enrollment in the MELT trial. No other adverse events will be reported unless deemed to related to the study by the Principal Investigator.

STUDY PROCEDURES

- ▣ This is a randomized, double blinded, placebo-controlled single center study of at least 200 patients who are admitted to Aultman Hospital with clinical decompensated Class III-IV congestive heart failure.
- ▣ All patients will receive standard heart failure therapy, including but not restricted to diuretics, digoxin, angiotensin converting enzyme inhibitors or angiotensin II receptor blockers, beta blockers, aldosterone antagonists, hydralazine, and/or nitrates, at the discretion of the treating physician.
- ▣ After informed consent is obtained, patients will be randomized 1:1 to the treatment arm or placebo arm.
- ▣ Two doses of study drug will be administered. The first dose will be given as soon as possible following enrollment, but within 6 hours of the first intravenous diuretic

administration. This will be considered Day 0. The second dose will be administered 24 hours after the first dose of study drug. This will be considered Day 1. Patients and physicians will be blinded to the administered drug (metolazone vs. placebo). In the event of unforeseen circumstances the patient does not receive both doses of study drug (i.e. early discharge or emergent surgery), they will be deemed inevaluable. See Analysis Populations section below.

- ▣ Study drug assignment will be randomized and distributed by a delegated pharmacist after the patient is consented and enrolled in the trial.
- ▣ Specific guidance/recommendations regarding diuretic therapy will be provided (documented in detail below) but will be at the discretion of the treating physician.
- ▣ We will collect data on demographics, co-morbidities, clinical presentations and outcomes with Metolazone administration with patient follow up within seven (± 3) days and 30 (± 7) days post discharge.
- ▣ BMP, magnesium and CBC will be collected daily or as clinically indicated at the discretion of the treating physician..
- ▣ BNP will be collected on admission and Day 2. For the first ten (10) patients, a BNP will be collected at discharge.
- ▣ Patients will be preferred to have an indwelling urinary catheter to collect accurate output measurements. If patient agreeable, the catheter will be placed upon enrollment unless already in place. Total urinary output will be measured at 48 hours after from administration of first intravenous diuretic.
- ▣ Daily intake, urine output and standing weights will be measured for the entire length of the hospital stay. The total urine output and negative fluid balance will be measured at 48 hours from administration of first intravenous diuretic (primary endpoint).
- ▣ Total dose of diuretics administered in both groups will be monitored and compared with total urine output at 48 hours (primary endpoint). Urine output will be adjusted based on total loop diuretic dose beginning from administration of first intravenous diuretic (analysis of covariance).
- ▣ Study drug will be administered as soon as possible after enrollment in the study and this will be conveyed clearly to the emergency staff prior to starting the study to avoid unnecessary delays. The time interval between the administration of loop diuretic and the dose of study drug will be tracked as well and adjustments made accordingly in the final analysis.

Inclusion/Exclusion Criteria

Inclusion Criteria

- ▣ Age 18 years or older

- ▣ Current hospitalization for chronic congestive heart failure with admission up to 48 hours prior to inclusion.
- ▣ Chronic heart failure will be defined as requiring treatment for a minimum of 30 days prior to current admission, NYHA Class III or IV at the time of hospitalization, and left ventricular ejection fraction less than or equal to 40% within one year or evidence of heart failure with preserved ejection fraction and evidence of diastolic dysfunction on echocardiogram.
- ▣ Admitted with clinical decompensated heart failure based on history, physical exam, and parameters indicating extracellular volume expansion such as including JVP \geq 8 cm of water and 1+ or greater peripheral edema
- ▣ Is able to be dosed with study medication within six (6) hours of first dose of IV diuretics

Exclusion Criteria

- ▣ Baseline severe hypotension defined as mean arterial pressure (MAP) less than 55
- ▣ Creatinine clearance less than 20 ml/min or creatinine greater than 2.5 mg/dl.
- ▣ Serum sodium less than 128 meq/L.
- ▣ Serum Potassium < 3.0 meq/L.
- ▣ Known adverse reaction to metolazone
- ▣ Inability to take oral medications
- ▣ Severe Aortic Stenosis (AVA < 0.8cm²)
- ▣ History of Hypertrophic obstructive cardiomyopathy
- ▣ Metastatic Carcinoma per history
- ▣ Severe COPD, FEV < 1L
- ▣ Severe dyspnea requiring prolonged CPAP,BIPAP or intubation

Subject Population

Recruitment

- ▣ At least 200 patients who are admitted with acute decompensated heart failure will be identified in the Emergency Room, Outpatient Clinic, 4 South, or Cardiac Care Unit.
- ▣ Patients included in the study will receive standard heart failure therapy including but not restricted to digoxin, angiotensin converting enzyme inhibitors or angiotensin II receptor blockers, beta blockers, aldosterone antagonists, hydralazine, and/or nitrates, at the discretion of the treating physician.
- ▣ After informed consent is obtained patients will be randomized 1:1 to the treatment arm or placebo arm.

- ▣ For the participating patients, they will be recommended to at least receive their (total daily outpatient dose of furosemide) x1.25 intravenously.
- ▣ With equivalent conversion which would be 2:1 for torsemide and Lasix and 40:1 for bumex and Lasix, we will give at least 1.25 x intravenous dose of Lasix if they are taking torsemide or bumex as part of their outpatient regimen.
- ▣ If enrolled in the study, the first dose of study drug will be given as soon as possible following enrollment, but within 6 hours of the first IV dose diuretics. The second dose will be administered 24 hours after the first dose of study drug..
- ▣ Electrolytes will be repleted per the treating physician.
- ▣ Drug administration will be held in patients with severe hypotension (MAP less than 55).

STATISTICAL ANALYSIS

Statistical Methods

- ▣ Power Analysis: In the DOSE trial urine output at 72 hours was 4200ml with a standard deviation of 3200 ml.
- ▣ With 1:1 randomization, there is a power of more than 80% to detect a difference of 3000-4000 ml between the groups at 48 hours and at least 200 patients will be enrolled to achieve statistical significance.
- ▣ The demographics to the two groups will be compared with Fischer's exact T-test to ensure the validity of the randomization.
- ▣ Primary and secondary outcomes will be collected and compared with the Student's T-test.
- ▣ Appropriate subgroup analyses will be done and outcomes will be presented by Kaplan Meier plots.

Analysis Populations

- ▣ The Evaluable Population for the primary, secondary, and exploratory endpoints will include all randomized subjects who receive both doses of the study drug, and complete the 48 hour evaluation period. The efficacy analysis will be based on the Evaluable Population.
- ▣ If a patient does not receive both doses of study drug or complete the 48 hour evaluation period they will be considered inevaluable, however, this will not be classified as a protocol deviation.
- ▣ The Safety Endpoints will include all randomized subjects who receive at least one dose of the study drug.

Data and Safety Monitoring

A data safety monitoring committee will be assigned to review each case for eligibility, adherence to the protocol, occurrence of adverse events, and accuracy of data. This will be completed on a regular basis. The first review will be conducted after enrolling the first 100 patients. Regular reviews will be scheduled at increments of 50 randomized patients until enrollment goals are met. Unscheduled random chart audits will also be performed to ensure data integrity. Any deficiencies found during these reviews will be addressed and reported to necessary parties.

All study related data will be anonymized and secured via password access being strictly confidential to the investigators. The stored data will be kept in locked cabinets at all times with limited access.

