MELT-HF NCT02620384

MEtolazone as Early add on Therapy for acute decompensated Heart Failure.

A single center pilot study.

[name]

STATISTICAL ANALYSIS (UPDATED 12/4/2018)

Statistical Methods

- ▣ Power Analysis: In the DOSE trial urine output at 72 hours was 4200ml with a standard deviation of 3200 ml.
- ▣ With 1:1 randomization, there is a power of more than 80% to detect a difference of 3000-4000 ml between the groups at 48 hours and at least 200 patients will be enrolled to achieve statistical significance.
- ▣ The demographics to the two groups were compared with Student's T test for continuous variables and Chi Square for categorical variables. There were no significant differences in age, gender, race or NYHA enrollment.
- ▣ Primary and secondary outcomes were compared with Student's T tests and Repeated Measures ANOVA (for longitudinal data) with between subjects variable.

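### No pre-randomisation covariate is planned for 48-hour urine output or fluid balance, and the plan's statements on adjustment conflict

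*Protocol*

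**What the plan says.** Three places bear on how 48-hour urine output and fluid balance are compared.

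- **Protocol, Statistical Methods:** "Primary and secondary outcomes will be collected and compared with the". The test this sentence goes on to name is a t-test, and it names no covariate.
- **Protocol, Study Procedures:** "Urine output will be adjusted based on total loop diuretic dose beginning from administration of first intravenous diuretic (analysis of covariance"). For the final analysis, the same section adds: "The time interval between the administration of loop diuretic and the dose of study drug will be tracked as well and adjustments made accordingly". It does not say how.
- **SAP, Statistical Methods (updated 12/4/2018):** "Primary and secondary outcomes were compared with Student's T tests and Repeated Measures ANOVA (for longitudinal data) with between subjects variable". The analysis of covariance is not carried forward.

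No section says which of these is the primary analysis, and none names a pre-randomisation covariate.

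Baseline values are nevertheless to hand. Creatinine and heart-failure type (reduced or preserved ejection fraction) must be known to apply the eligibility criteria. For BNP, Study Procedures states: "BNP will be collected on admission and Day 2". The outpatient loop-diuretic dose is needed for the dosing guidance under Recruitment ("they will be recommended to at least receive their (total daily outpatient dose of furosemide) x1.25 intravenously"), but it is not listed as a data item.

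**The concern.** There are two linked problems.

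First, the plan has no single primary analysis of its primary endpoint. The t-test, the loop-dose analysis of covariance and the interval adjustment can give different estimates. Nothing fixes in advance which one counts.

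Second, the only covariates the plan names are not baseline patient characteristics. Total loop dose is counted from the first intravenous dose through 48 hours, is set by the treating physician, and is listed as a secondary endpoint. If study drug changes urine output, physicians may change the loop dose in response. Conditioning on that dose can then bias the estimate of the effect of assignment. The interval ends when study drug is given, which is after randomisation, and it is also listed as a secondary endpoint.

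Meanwhile, baseline values that could safely reduce the error variance are left unused. The expected variation is large: the plan quotes an SD of 3200 ml against a mean of 4200 ml. What is at stake is the width of the confidence interval and the power for effects smaller than the planned one.

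**Working it through.** **Inputs**

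- SD 3200 ml: Statistical Methods, both documents. It is a 72-hour figure; no 48-hour SD is given.
- 200 patients at 1:1, so 100 per arm: same sections.
- Planned difference 3000-4000 ml, power more than 80%: same sections.
- 4899 − 3575 = 1324 ml: the 72-hour difference between dose strategies quoted in the protocol under Previous Trials.
- Alpha is not stated. Two-sided 0.05 is assumed.
- No rate of inevaluable patients is stated. Zero is assumed unless noted.
- R-squared of the baseline covariates with 48-hour urine output is not in the documents. 10, 20 and 30% are assumed.
- No SD is given for fluid balance, so the figures below are for urine output only.

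**Step 1: the plan's own figure.** By the noncentral t distribution with SD 3200 ml, 80% power needs 19 per arm for 3000 ml and 12 per arm for 4000 ml. With 100 per arm, power exceeds 99.99% across that range. The claim of more than 80% is literally true, but 200 patients does not follow from it.

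**Step 2: unadjusted precision.** SE = SD × √(2/n) = 3200 × √(2/100) = 453 ml. The 80%-power detectable difference is 2.815 × 452.5 = 1274 ml. The normal approximation, with multiplier 2.802, gives 1268 ml.

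**Step 3: adjusted precision.** Residual SD = 3200 × √(1 − R²), and the SE scales in the same way. The equivalent unadjusted sample size is 200/(1 − R²).

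| R² | Residual SD (ml) | SE (ml) | 95% half-width (ml) | Detectable at 80% (ml) | Power at 1324 ml | Equivalent N |
|---|---|---|---|---|---|---|
| 0 | 3200 | 453 | 892 | 1274 | 83% | 200 |
| 10% | 3036 | 429 | 847 | 1209 | 87% | 222 |
| 20% | 2862 | 405 | 798 | 1140 | 90% | 250 |
| 30% | 2677 | 379 | 747 | 1066 | 94% | 286 |

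Four covariates reduce the error degrees of freedom from 198 to 194. That moves each detectable difference by less than 1 ml. The proportional fall in SE (5, 11 and 16%) does not depend on the SD, so the 72-hour source affects only the millilitre figures.

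**Step 4: fewer evaluable patients.** The efficacy analysis excludes patients who miss a dose or the 48-hour evaluation. If 80 per arm remained (an illustration, not a documented rate), power at 1324 ml would be 74% unadjusted and 83% with R² of 20%.

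**Step 5: timing of each covariate**

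| Variable | Fixed before randomisation? | In the planned analysis? |
|---|---|---|
| Admission creatinine | Yes | No |
| Heart-failure type | Yes | No |
| Admission BNP | Yes | No |
| Home loop-diuretic dose | Yes, if recorded | No |
| Total loop dose to 48 hours | Mostly not | Study Procedures only |
| Loop-to-study-drug interval | No | Study Procedures only, method not given |

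**The case against.** The strongest case on the other side has four parts.

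**The plan is not simply unadjusted.** A reader of the two Statistical Methods sections might infer that the primary comparison is an unadjusted t-test and nothing more. The documents do not support that, because Study Procedures plans two adjustments. This stands: the defect is an unresolved conflict together with the absence of any baseline covariate. If the loop-dose analysis of covariance governs, the gains above are also measured against the wrong comparator. Recommended dosing is tied to home dose, so total loop dose may already absorb part of what home dose would explain. That does not rescue it as a covariate, because it mostly arises after randomisation.

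**The t-test is valid.** In a 1:1 randomised comparison, chance imbalance is already reflected in its standard error. This stands. Adjustment is a gain in efficiency, not the repair of an error.

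**The size of the gain is assumed.** No document shows that creatinine, BNP, heart-failure type or home dose predicts 48-hour output. At the planned 3000-4000 ml the gain in power is nil for practical purposes, and at 1324 ml the unadjusted test already has 83% power. This stands as a limit on size. It does not remove the benefit for interval width, nor for effects below the planned range. That range is 71 to 95% of the quoted mean 72-hour output (3000/4200 and 4000/4200).

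**It may be too late.** The SAP is in the past tense and reports baseline comparisons. A reader might infer that outcomes had been unblinded by then. The text does not establish this, but it means the status of any new model must be declared.

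**Conclusion.** The point holds as a recommended improvement. The plan gives conflicting accounts of how its primary endpoint is analysed, names covariates that are fixed mostly or wholly after randomisation, and uses none fixed before it. Reading the plan as invalid or underpowered for its stated target would go too far: the t-test is valid, and power at 3000-4000 ml exceeds 99.99% with or without adjustment.

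The size of the precision gain depends on an R-squared that the documents do not give. Over the assumed 10 to 30%, it is worth 22 to 86 extra patients on a base of 200, and 4 to 11 percentage points of power at 1324 ml. Confidence is high that no baseline covariate is planned and that the sections conflict. It is moderate on the size of the gain. The possible bias from conditioning on total loop dose cannot be sized from the documents, but it is reason enough to keep that variable out of the primary model.

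**What to change.** 1. Reconcile Study Procedures and both Statistical Methods sections into one stated primary analysis of 48-hour urine output, and the same for fluid balance.
2. Make it a linear model with arm plus admission creatinine, heart-failure type and admission BNP. Add home loop-diuretic dose in furosemide equivalents if it was recorded, coded zero for patients not on one.
3. Report the adjusted mean difference with its 95% CI. Keep the unadjusted t-test as a sensitivity analysis.
4. Do not use total loop dose as a covariate in the primary model; report it by arm as the secondary endpoint it already is. State the purpose and method of any interval adjustment and keep it outside the primary model.
5. State whether outcome data had been unblinded when the change is made. If so, label the adjusted model post hoc or sensitivity.

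The cost is revised wording in three places, a few lines of code and about four degrees of freedom. Creatinine, heart-failure type and BNP need no new data. Whether home loop dose was recorded must be checked.

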Appendix 1: Modified Borg Scale

SCALE	SEVERITY
0	No Breathlessness* At All
0.5	Very Very Slight (Just Noticeable)
1	Very Slight
2	Slight Breathlessness
3	Moderate
4	Some What Severe
5	Severe Breathlessness
6	
7	Very Severe Breathlessness
8	
9	Very Very Severe (Almost Maximum)
10	Maximum

MELT-HF NCT02620384

MEtolazone as Early add on Therapy for acute decompensated Heart Failure.

A single center pilot study.

[name]

STATISTICAL ANALYSIS (UPDATED 12/4/2018)

Statistical Methods

- ▣ Power Analysis: In the DOSE trial urine output at 72 hours was 4200ml with a standard deviation of 3200 ml.
- ▣ With 1:1 randomization, there is a power of more than 80% to detect a difference of 3000-4000 ml between the groups at 48 hours and at least 200 patients will be enrolled to achieve statistical significance.
- ▣ The demographics to the two groups were compared with Student's T test for continuous variables and Chi Square for categorical variables. There were no significant differences in age, gender, race or NYHA enrollment.
- ▣ Primary and secondary outcomes were compared with Student's T tests and Repeated Measures ANOVA (for longitudinal data) with between subjects variable.
